1.1 Introduction

In developed countries, back pain ranks among the top 10 complaints that bring participants to see a doctorⁱ yet in 84% of cases, no specific cause can be found.^{ii, iii} Where the pain is of lumbar origin, the diagnosis can usually be established using medical imaging techniques and neurological testing. The sacroiliac joints, just below the lumbar spine, are difficult to visualize using imaging techniques, except in cases of ankylosing spondylitis, and tests for sacroiliac dysfunction are not reliable^{iv, v, vi} nor do these diagnostic techniques suggest therapeutic options.^{vii, viii} This may be why the sacroiliac joints have been neglected as a possible cause for low back pain^{ix}.

In my family practice with a special interest in pain, in order to better determine the cause of this frequent complaint, I developed a new, quick and easy way to examine this joint, the Sacroiliac Forward Flexion Test (SIFFT). This test determines the location of the posterior superior iliac spines (PSISs): many of those with back pain were very tender to pressure applied just below one or both of these PSISs and pointed to this as being where they had the most pain. This corresponds to the long dorsal sacroiliac ligament, which would be painful, should there be a malrotation of the corresponding sacroiliac joint. To assess for malrotation, I put a mark under each of the PSISs, and used a carpenter's level to test whether they were at the same level.^x I also test the participant for leg length discrepancy by measuring from the umbilicus to the medial malleolus bilaterally as this can affect the PSIS levels.

A malrotation of the sacroiliac joints puts excess strain on the muscles stabilizing this joint and these usually develop tendinitis. The gluteus medius and minimus, join the sacrum and ileum to the greater trochanter where malrotation sufferers are often diagnosed as having trochanteric bursitis. The iliopsoas joins the ilium to the lesser trochanter causing groin pain with SI malrotation. The quadratus lumborum joins the ileum to the lumbar lateral processes and the 12th rib, and a malrotation of the ilium can also cause a quadratus lumborum tendinitis. The biceps femoris joins the ischium to the head of the fibula and tendinitis of this muscle is often the cause of pain on sitting and in

the knee for those with sacroiliac malrotation. The presence of tenderness where these pelvic stabilizer muscles attach will be documented in this study.

In 2018 I did a chart review of 180 cases of low back pain in which I tested those who did not have lumbar pain using the SIFFT^x. I treated them with the appropriate exercise depending on the direction of the sacroiliac rotation. From this review, I found 16 cases of pain coming from the lumbar spine (9%). Of the remaining 164 given the appropriate 2 minute exercises, 78% found pain relief of which two thirds left the office entirely pain free. At that time, I also prescribed a pelvic support belt as, generally, a malrotated pelvis is an unstable pelvis^{xi}. As soon as the pelvis becomes malrotated again, the pain recurs. As the corrective exercise and pelvic support belt are two different treatments, the current research project will study them first separately for one month, then on follow-up after they have been used together for one month.

The aim of this study is to determine whether the pain relief and improved back function is temporary or if it can be reproduced and sustained by the patient at home, as needed with these two treatments. In order to test the effectiveness of each treatment alone and when they are combined, two sub-studies will be carried out as follows:

The first study is a superiority trial with a delayed control.

Population: ambulatory people between the ages of 19 and 90 suffering from low back pain, not of lumbar spine or hip origin, for at least three months.

Intervention 1 : teaching participants how to detect pelvic malrotation using the SIFFT then prescribing a two-minute exercise to correct pelvic malrotation, depending on its direction.

Intervention 2: prescribing a pelvic support belt to stabilize the pelvis.

Control: waiting list for one month, using usual treatments such as medications, alcohol and other drugs, chiropractic and other manipulation and physical therapy.

Outcome: a clinically significant change in Brief Pain Inventory (BPI) NRS pain score or in Oswestry disability Index (ODI) for low back pain.

Time: outcomes measured at baseline and after one month of using the assigned treatment at home.

The second study is a one month follow-up of the combined treatments.

Population: all previous study participants

Intervention: teaching all participants how to detect pelvic malrotation using the SIFFT then a two-minute exercise to correct pelvic malrotation depending on its direction followed by prescription of a pelvic support belt.

Control: BPI NRS pain severity score and ODI at one month assessment

Outcome: a clinically significant change in BPI NRS pain severity score or ODI

Time: outcomes measured at the one month assessment and after one month of using the combined treatments at home.

The effects of the SIFFT and associated exercises are important to investigate as they may prove to be both diagnostic and therapeutic. When someone experiences back

pain relief from an exercise to correct sacroiliac malrotation, this indicates that their back pain is not coming from their lumbar spine, but from a malrotated sacroiliac joint. The knowledge and relief from this simple test may help avoid unnecessary medical imaging and spinal surgery. If back pain relief is sustained with the use of a pelvic support belt, then the pain can be ascribed to pelvic instability^{xii} ^{xiii}. A better understanding of the potential sustained effects of these two treatments has great potential to improve care and reduce costs for patients with low back pain^{xiv}.

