1.2. Hypotheses

The first study aims to find out if the recently developed exercises or the use of a pelvic support belt provide more than short term pain relief in the doctor's office:

Primary Hypotheses for the first study:

1. At 1 month, there will be significantly greater improvement in the ODI for low back pain score: at least 10% greater in those who are in treatment group 1 and are immediately taught how to perform the SIFFT followed by the appropriate exercise when compared to those on the waiting list for one month prior to being treated.
2. At 1 month, there will be significantly greater improvement in the ODI for low back pain score: at least 10% greater in those who are in treatment group 2 and are immediately given the pelvic support belt when compared to those on the waiting list for one month prior to being treated.

Secondary Hypotheses for the first study:

- 1 At 1 month, there will be significantly greater improvement in the BPI NRS pain severity score in those who are in treatment group 1 and are immediately taught how to perform the SIFFT followed by the appropriate exercise when compared to those on the waiting list for one month prior to being treated.
- 2 At 1 month, there will be significantly greater improvement in the BPI NRS pain severity score in those who are in treatment group 2 and are immediately fitted with a pelvic belt when compared to those on the waiting list for one month prior to being treated.

The follow-up study aims to find out if the recently developed exercises together with the use of a pelvic support belt provided more pain relief than each individual treatment:

Primary Hypothesis for the follow-up study:

- 1 At 2 months, there will be significantly greater improvement in the ODI for low back pain score compared to their one-month score in all participants.

Secondary Hypothesis for the follow-up study:

- 1 At 2 months, there will be significantly greater improvement in the BPI NRS pain severity score compared to their one-month score in all participants.

2.0 Recruitment:

Participants making a first appointment at the clinic for back pain will be in contact with my medical office assistant, [name], and invited to participate in this study. If they would like to participate, she will send them the consent form and eligibility questionnaire. If they are eligible, she will schedule them for their first visit.

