5.0 Statistics

5.1 Outcome Measures

5.1.1A Primary Outcomes For the First Study

- difference in the change in ODI score in the initial treatment visit questionnaire and at the assessment visit one month later in the control group compared to the change from the treatment visit questionnaire to the 1 month assessment follow-up visit in the immediate SIFFT and exercise treatment group.
- difference in the change in ODI score in the treatment visit questionnaire and at the assessment visit, one month later, in the control group compared to the change from the treatment visit questionnaire to the 1 month assessment follow-up visit in the immediate pelvic support belt treatment group.

5.1.2A Secondary Outcomes For the First Study

- difference in the change in BPI NRS pain severity scores in the treatment visit questionnaire and at the assessment visit, one month later, in the control group compared to the change from the treatment visit questionnaire to the 1 month follow-up assessment visit in the immediate SIFFT and exercise treatment group.
- difference in the change in BPI NRS pain severity scores in the treatment visit questionnaire and at the assessment visit, one month later, in the control group compared to the change from the treatment visit questionnaire to the 1 month follow-up assessment visit in the immediate pelvic support belt treatment group.

5.1.1B Primary Outcome For the Follow-up Study

- difference in the change in ODI score in the assessment visit questionnaire and at the reassessment visit, two months later, for all groups.

5.1.2B Secondary Outcome For the Follow-up Study

- difference in the change in BPI NRS pain severity scores in the assessment visit questionnaire and at the reassessment visit, two months later, for all groups.

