5.1.3 Other Measurements

- Change in pain level, immediately before and after the corrective exercises at
 - the treatment visit for members of group 1
 - the one-month follow-up assessment visit.
 - the two month reassessment visit
- Change in average pain level between the
 - treatment visit
 - and the one-month follow-up visit.
- Number of times the exercise was used per week
- Perceived effectiveness of the exercise
 - when first used with the physician
 - one month later,
 - and two months later for group 1
- How often the pelvic support belt was used during the day at the one month follow-up assessment visit for group 2.
- How often the pelvic support belt was used during the day at the 2 month reassessment visit for all participants.
- How often the pelvic support belt was used during the night at the follow-up assessment visit for group 2.
- How often the pelvic support belt was used during the night at 2 month reassessment visit for all participants.
- Perceived effectiveness of the pelvic support belt when first used and after one month of use for all participants.
- perceived effectiveness of the pelvic support belt when first used and after two months of use for group 2.

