5.2 Statistical Analysis

Data will be analyzed using PASW Statistics 18, Release 18.0.0, IBM. Analysis will be performed by intention-to-treat. Descriptive statistics (mean value \pm standard deviation (SD)) will be calculated for outcome variables at each time point. Baseline between-group data will be analyzed for significant differences by t-tests for nominal variables and Pearson chi square tests for categorical variables. Baseline characteristics will be included in the model as covariates for those variables with a significant between group difference. Analyses of covariates will be applied to compare the groups for magnitude of change in the 0-10 NRS pain score and Oswestry Disability Index between baseline and each follow-up time point (0, 1 and 2 months). A two-tailed P value $<.05$ will be used as the statistical significance level.

- a Pearson's chi-square-test will be done to assess the significance of the difference in Oswestry low back disability score over a 1 month period between

those who are treated with the immediate SIFFT and exercise treatment group, the immediate pelvic support belt group and those who are in the observation group.

- A second Pearson's chi-square will be done to assess the significance of the difference in BPI NRS pain severity score over a 1 month period between those who are treated with the immediate SIFFT and exercise treatment group, the immediate pelvic support belt group and those who are in the observation group.
- A student t-test will be done to assess the significance of the difference in ODI score over a one month period when both treatments are used simultaneously.
- A student t-test will be done to assess the significance of the difference in BPI NRS pain severity score over a one month period when both treatments are used simultaneously.
- The average and standard deviation for all the other data will be calculated and reported on.

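### The aim is sustained relief, but no planned outcome measures whether the month-1 benefit is held; the follow-up test counts only further improvement, pooled with the waiting-list group's first treatment

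*Combined protocol and SAP*

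**What the plan says.** Section 1.1 sets the overall aim: to "determine whether the pain relief and improved back function is temporary or if it can be reproduced and sustained by the patient at home". It also draws a diagnostic conclusion from durability, since relief that lasts with the belt is to be taken as evidence of pelvic instability. The two treatments are to be handled in sequence: "study them first separately for one month, then on follow-up after they have been used together for one month".

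The first study compares exercise alone and belt alone with a waiting list at one month. Section 1.2 describes it as asking whether they "provide more than short term pain relief in the" doctor's office. At the one-month visit every group is given both treatments (3.3), and for group 3 these are the first study treatments (3.2.1).

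The follow-up study takes as its control each participant's "BPI NRS pain severity score and ODI at one month assessment" (1.1). Its declared aim in 1.2 is whether the two treatments together relieve more than either one singly. Its primary hypothesis is "significantly greater improvement in the ODI for low back pain score compared to their one-month score in all participants". The matching outcome in 5.1.1B is "difference in the change in ODI score in the assessment visit questionnaire and at the reassessment visit, two months later, for all groups", and 5.2 tests by Student t-test the "difference in ODI score over a one month period when both treatments are used simultaneously". The BPI is handled in the same way as the secondary outcome.

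Section 5.2 also plans an analysis with covariates that compares the groups on change from baseline at 0, 1 and 2 months, and means with SDs at each time point. Section 5.1.3 lists exercise effectiveness at two months for group 1, and "perceived effectiveness of the pelvic support belt when first used and after two months of use for group 2".

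**The concern.** A question about whether relief lasts needs a quantity that distinguishes benefit kept from benefit lost. None of the listed outcomes does this. In the follow-up analysis, a group 1 or 2 participant who improved by month 1 and stayed improved has zero change, exactly like one who never improved.

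Pooling adds a second difficulty. For groups 1 and 2 the month-1 score follows one treatment. For group 3 it follows none. The pooled change therefore mixes the effect of adding a second treatment with the effect of starting treatment.

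At stake is how the follow-up result will be read. A positive result could be taken as evidence that relief lasts, or that the combination beats each treatment alone, when it came from group 3. A null result could be taken as relief fading when it was fully held. The two-month ratings in 5.1.3 could likewise be read as the durability of a single treatment, although the other treatment had been added a month before.

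**Working it through.** **Inputs from the documents.** Three groups of 20, 3 × 20 = 60, which agrees with 2.2; the number is justified only as a pilot. Two-sided significance level 0.05 (5.2). No SD, power or follow-up effect size is given. The only effect named is 10% on the ODI for the first study (1.2), without saying whether this means points or a relative percentage.

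**Assumptions.** SD of individual ODI change 8 to 20 points; group 3 improvement of 10 points (one reading of the 10%) or 15 points; the t-test is paired, that is, a one-sample test on month-1 to month-2 change. Improvement is counted as positive.

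**Step 1: what the change means in each group.**

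| Group | To month 1 | Month 1 to 2 | Meaning of the change |
|---|---|---|---|
| 1 | exercise | both | holding, plus adding the belt |
| 2 | belt | both | holding, plus adding the exercise |
| 3 | waiting list | both | first treatment |

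With equal groups the pooled mean is (d1 + d2 + d3)/3, so one third of the weight lies on first treatment.

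**Step 2: nobody changes after month 1.** Then d1 = d2 = d3 = 0, and the test declares improvement only by chance: 2.4% to 2.6% of simulated trials (40,000 per setting), whatever was gained by month 1.

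**Step 3: groups 1 and 2 hold, group 3 improves by 10, SD 10.**
- Pooled mean: (0 + 0 + 10)/3 = 3.33.
- Variance from the differing group means: (2 × 3.33² + 6.67²)/3 = 22.2. Total SD: √(100 + 22.2) = 11.1.
- Estimated standard error: 11.1/√60 = 1.43. The critical value of t on 59 df is 2.00, so the mean must exceed about 2.86.
- Group sizes are fixed, so the mean varies with standard error 10/√60 = 1.29. (3.33 − 2.86)/1.29 = 0.37, giving a probability of about 64%. The simulation gives 64%.

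**Step 4: the same test over the range of SDs (simulated % significant).**

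| Change in groups 1 and 2 / group 3 | SD 8 | 10 | 12 | 15 | 18 | 20 |
|---|---|---|---|---|---|---|
| 0 / +10 | 82 | 64 | 50 | 36 | 27 | 22 |
| 0 / +15 | 98 | 92 | 81 | 64 | 50 | 43 |
| −2 / +15 | 76 | 61 | 48 | 36 | 28 | 24 |

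In the last row groups 1 and 2 are losing benefit, yet the pooled test still often reports improvement.

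**Step 5: does anything else in the plan fill the gap?** The analysis with covariates reaches month 2 but compares the groups with each other. By then all have both treatments. A difference between groups reflects different exposure histories, and no difference is compatible with all holding or all losing. Section 5.1.3 lists change in average pain only up to the one-month visit. Means at each time point give raw material, but not within-person change with its uncertainty.

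**Step 6: precision of the repair.** For one group of 20 the 95% CI half-width is 2.093 × SD/√20: 3.7 points at SD 8, 4.7 at SD 10, 9.4 at SD 20. A formal test that groups 1 and 2 together (n = 40) lost no more than an illustrative 5 points, with true loss zero and one-sided level 0.025, has power 97%, 87%, 73%, 54%, 40% and 34% at SD 8, 10, 12, 15, 18 and 20. Estimates with intervals are therefore the realistic aim.

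**The case against.** The strongest reply is that the follow-up study has its own declared aim, combination versus each single treatment, and that change from month 1 suits that aim. This stands: the mismatch is with the overall aim in 1.1, and the outcome is not wrong in kind for the follow-up question. Even for that question, though, pooling in group 3 blurs the answer, because group 3 had neither treatment before month 1.

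Second, the first study does test relief at home, to one month, against a concurrent randomized control. This also stands. Durability is untested only beyond month 1.

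Third, following each treatment alone for one month is an openly stated design choice, and the ODI and BPI are collected at every visit. True; what is missing is an outcome and a reporting rule, not data.

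Two stronger readings are tempting. A reader might infer that fully sustained relief makes the follow-up primary test fail. That is right for the contribution of groups 1 and 2, but not for the trial: Step 4 shows that group 3 can carry the test. A reader might also take the chart review in 1.1 (78% relieved, two thirds of those pain free) and infer that a similar share would be at the ODI floor by month 1. The documents do not support this. Those figures describe pain on leaving the office after supervised exercise, not ODI and not month 1. They do not isolate belt-only use, and carrying them forward assumes the persistence under study.

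**Conclusion.** The concern holds in this form: no outcome measures maintenance of the month-1 benefit, and the pooled follow-up test can be positive or null for reasons unrelated to it. With groups 1 and 2 exactly level, the chance of a significant pooled result runs from about 2.5% if group 3 is level too, to 22–82% if group 3 improves by 10 points and 43–98% if it improves by 15. These figures rest on assumed SDs of 8 to 20 points, assumed gains and a paired test. The structural point, that held benefit contributes zero and group 3's first exposure is mixed in, needs none of those assumptions.

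It does not follow that the overall aim is untested or that the follow-up study must fail. The matter is one of outcome definition and reporting in a 60-person pilot, and should be settled before the data are analysed.

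Separately, 5.1.1B and 5.1.2B, read literally, place reassessment two months after the assessment visit. Sections 1.1 and 5.2 give one month of combined use, and the contents list puts the third visit two months after the treatment visit. These statements must be reconciled.

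**What to change.** 1. In 5.1 and 5.2, report month-1 to month-2 change in ODI and BPI separately by original group with 95% CIs. Use all participants in groups 1 and 2 to address maintenance and added benefit. Do not restrict this to those who improved by month 1, because selecting on a noisy score would produce apparent loss by regression to the mean. Do not attribute group 3's change to adding a second treatment.
2. Add baseline-to-month-2 change by original group with 95% CIs, labelled as an uncontrolled description. Place it beside the further-improvement test, not in its stead; it can be positive despite partial loss after month 1.
3. State that no change from month 1 to month 2 is not to be read as loss of benefit. Give the number of carried-forward month-2 values in each group, since the rule in 3.5.1 sets their change to exactly zero and could pass for maintenance.
4. Limit conclusions on exercise alone and belt alone to one month, and label the two-month ratings in 5.1.3 as made while using both treatments.
5. Reconcile the interval in 5.1.1B and 5.1.2B with 1.1 and 5.2.

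The cost is wording and one extra table, with no new visits, participants or measurements. The price is precision: intervals rest on 20 per group instead of 60, and the month-2 description has no untreated comparator.

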1.2. Hypotheses

The first study aims to find out if the recently developed exercises or the use of a pelvic support belt provide more than short term pain relief in the doctor's office:

Primary Hypotheses for the first study:

1. At 1 month, there will be significantly greater improvement in the ODI for low back pain score: at least 10% greater in those who are in treatment group 1 and are immediately taught how to perform the SIFFT followed by the appropriate exercise when compared to those on the waiting list for one month prior to being treated.
2. At 1 month, there will be significantly greater improvement in the ODI for low back pain score: at least 10% greater in those who are in treatment group 2 and are immediately given the pelvic support belt when compared to those on the waiting list for one month prior to being treated.

Secondary Hypotheses for the first study:

- 1 At 1 month, there will be significantly greater improvement in the BPI NRS pain severity score in those who are in treatment group 1 and are immediately taught how to perform the SIFFT followed by the appropriate exercise when compared to those on the waiting list for one month prior to being treated.
- 2 At 1 month, there will be significantly greater improvement in the BPI NRS pain severity score in those who are in treatment group 2 and are immediately fitted with a pelvic belt when compared to those on the waiting list for one month prior to being treated.

The follow-up study aims to find out if the recently developed exercises together with the use of a pelvic support belt provided more pain relief than each individual treatment:

Primary Hypothesis for the follow-up study:

- 1 At 2 months, there will be significantly greater improvement in the ODI for low back pain score compared to their one-month score in all participants.

Secondary Hypothesis for the follow-up study:

- 1 At 2 months, there will be significantly greater improvement in the BPI NRS pain severity score compared to their one-month score in all participants.

2.0 Recruitment:

Participants making a first appointment at the clinic for back pain will be in contact with my medical office assistant, [name], and invited to participate in this study. If they would like to participate, she will send them the consent form and eligibility questionnaire. If they are eligible, she will schedule them for their first visit.

If not enough potential participants present at the office spontaneously, an email will be sent to all family physicians, rehabilitation specialists, neurosurgeons and neurologists associated with Lions Gate Hospital with information about the study.

Information about the study will also be posted on Facebook, Instagram and Twitter, which will refer potential participants to a website about the study. People will be warned that if they choose to post to the page, or “like” the page, they will be publicly identified with the study and instructed to consult the website instead.

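### Both primary hypotheses claim an ODI gain over waiting list of 10% or more, but the 10% is undefined and no planned analysis uses it, so P<.05 alone cannot support that part of the claim

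*Combined protocol and SAP*

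**What the plan says.** Section 1.2 gives two primary hypotheses for the first study. Each asks for a significantly greater one-month ODI improvement than on the waiting list and attaches a size: "at least 10% greater in those who are in treatment group 1" for exercise and "at least 10% greater in those who are in treatment group 2" for the belt. The secondary and follow-up hypotheses carry no such figure.

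Section 5.1 defines the primary outcomes as the "difference in the change in ODI score in the initial treatment visit questionnaire" and at one month, control against each treatment group. It sets no 10% criterion.

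Section 5.2 contains these elements:
- A general comparison: "Analyses of covariates will be applied to compare the groups for magnitude of change in the 0-10 NRS pain score and Oswestry Disability Index".
- For the one-month ODI across the three groups, a Pearson chi-square that "will be done to assess the significance of the difference in Oswestry low back disability score over a 1 month period".
- For the combined-treatment month: "A student t-test will be done to assess the significance of the difference in ODI score over a one month period".
- One criterion for all: "A two-tailed P value $<.05$ will be used as the statistical significance level".

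It also plans means and SDs of the outcome variables at each time point. It mentions no margin, confidence interval, responder cut-point or minimum observed difference.

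Section 2.2 sets 20 per group as a pilot and does not use the 10%. Section 1.1 calls the first study a superiority trial and describes its outcome as a clinically significant change, with no number.

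**The concern.** Each primary hypothesis has two parts, significance and size. The plan has a rule for the first and none for the second. When the results arrive, nothing written in advance says whether the size condition was met, what it is measured in, or which estimate it applies to. The meaning of 10% could then be settled after the data are known. A P value below 0.05 could also be presented as support for the whole hypothesis when it bears only on whether the difference is zero. What is at stake is the wording of both primary conclusions, not the validity of the data.

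**Working it through.** **1. Where the 10% is used.** It appears in the two primary hypotheses in 1.2 and not in 2.2, 5.1 or 5.2. Every test in 5.2 has a null of no difference. The chi-square has no stated ODI categories and yields no mean difference. The covariate-adjusted comparison could yield one, but 5.2 does not ask for the estimate or its interval.

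**2. What 10% could mean.** Appendix 2 lists ten sections scored 0-5 (raw maximum 50) and gives no scoring rule.
- Points on a 0-100 scale: 10 points. Ten per cent of the raw maximum is 0.10 x 50 = 5 raw points, which is the same thing after rescaling.
- Relative to baseline, for an assumed ODI of 20-50: 0.10 x 20 = 2 to 0.10 x 50 = 5 points.
- Relative to the control group's change, if controls improve by an assumed 5 points: 0.10 x 5 = 0.5 point.

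The readings differ by a factor of up to 20 (10 / 0.5).

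**3. The plan's own figure.** The 20 per group has no stated SD, power or effect, so it cannot be reproduced. As a back-check, 20 per group gives 80% power for 10 points only if SD = 10 / [(1.960 + 0.842) x sqrt(2/20)] = 11.3.

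**4. What P<.05 shows if 10% means 10 points.** Inputs are n = 20 per group (2.2), two-sided 0.05 (5.2), and an assumed SD of ODI change. I use an unadjusted two-sample t comparison with 38 df as a stand-in for the adjusted model.

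Smallest significant observed difference = t(0.975, 38) x SD x sqrt(2/20) = 2.024 x 0.3162 x SD = 0.640 x SD.

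| Assumed SD | Smallest significant difference | P(significant), true difference 5 | P(significant and estimate <10), true difference 10 | Estimate needed for lower 95% limit of 10 |
|---|---|---|---|---|
| 12 | 7.7 | 25% | 23% | 17.7 |
| 15 | 9.6 | 18% | 5.8% | 19.6 |
| 18 | 11.5 | 14% | 0.6% | 21.5 |

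The third column is power from the noncentral t, with noncentrality 5 / (SD x 0.3162). The fourth is by simulation. The fifth is 10 plus the second column.

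Break-even: 0.640 x SD = 10 gives SD = 15.6. Below that, a significant result can show fewer than 10 points. Above it, a significant unadjusted estimate is at least 10. The SD that matters is the one observed in the trial, which is why the 0.6% at a true SD of 18 is not zero.

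Over a wider range, the smallest significant difference runs from 5.1 points (SD 8) to 12.8 (SD 20). The chance of significance at a true 5 points runs from 49% to 12%. Covariate adjustment may lower the SD that applies.

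**The case against.** The strongest reply is that the hypothesis joins two conditions, so a significant difference below 10% would simply not confirm it. That is a fair reading, perhaps the most natural one. A reader might infer that the plan would declare the hypothesis confirmed on P<.05 alone, but no section says so. What remains is that 5.2 gives no rule for the size condition. The planned means and SDs let a reader compute an observed difference in change. They do not give its interval, because SDs at separate visits do not determine the SD of change.

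Second, the numbers depend on an assumed SD and on one reading of 10%. This stands. Above an SD of about 15.6, a significant estimate below 10 points essentially disappears. At SD 15 the cut-off of 9.6 is practically 10. On a relative-to-baseline reading of 2-5 points, any significant estimate at SD 12-18 would already exceed the threshold. A reader might also infer that significant results would often come from effects half the claimed size. The 14-25% does not show this: it is the power at an assumed true difference of 5, not the share of significant results that come from such effects.

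Third, the obvious remedy, a lower 95% limit of at least 10 points, would turn a superiority trial into superiority by a margin that the documents never state. At SD 15 it would be met 2.5% of the time at a true difference of 10 and about 18% at a true 15. This too stands. Nor do the documents call 10 points the clinically important difference.

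That the study is a pilot is a weaker defence, since 1.2 still states tested hypotheses. It does favour keeping the 10% as a benchmark.

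**Conclusion.** The concern holds in a limited form. The size element of both primary hypotheses has no unit, no reference and no analysis attached to it, and the test named for the one-month ODI cannot supply an estimate. That much rests on the text alone. P<.05 against no difference therefore supports only an improvement greater than on the waiting list.

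The numerical illustration is conditional on 10% meaning 10 points on a 0-100 ODI and on an SD that the documents do not give. Under those assumptions, a significant result can fall short of 10 points when the SD is below about 15.6. A true difference of 5 points reaches significance in roughly one trial in seven (SD 18) to one in four (SD 12). This should be corrected before data are seen, because it governs how both primary conclusions are worded.

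**What to change.** - **Section 1.2:** the sponsor defines the 10%, either as points on the 0-100 ODI or as a relative change with its reference (baseline or control change), and states how the ODI is scored.
- **Section 5.2, estimate:** for exercise and belt separately, estimate the treatment-minus-waiting-list difference in one-month ODI change from the covariate-adjusted model, with its 95% CI. This replaces reliance on the chi-square for the primary ODI conclusion.
- **Section 5.2, interpretation:** state that P<.05 supports only an improvement greater than on the waiting list. Then either judge the 10% by setting the estimate and CI beside the defined threshold, or remove the figure from the hypotheses and keep it as an interpretive benchmark. A lower confidence limit at or above the threshold is needed only for a claim that the true difference is at least that large.

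The cost is a few sentences and a less favourable possible claim. No extra patients or data are needed.
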